### 7.4 Multicentre Analysis

The analysis of combined centers is the primary analysis of efficacy endpoints. A meta-analysis approach will be chosen to pool the center dependent results for statistical analysis and to investigate for heterogeneity in the strata (e.g. Whitehead, 2003).

### 7.5 Multiple Comparison

As this was an exploratory study no confirmatory hypotheses have to be tested

### 7.6 General Calculation Rules

Binary, categorical and ordinal parameters will be summarised by means of absolute and percentage numbers (including 'missing data' as valid category at visit 1). Numerical data will be

summarised by means of standard statistics (i.e. number of available data, mean, standard deviation, minimum, median, maximum, lower and upper quartile). Wherever useful, the summary statistics will be presented by stratification according to centers and/or visit. In addition, adequate figures (e.g. bar charts, Box-Whisker-Plots) will be presented to summarise the results for some parameters.

All statistical tests will be performed two-sided and will be interpreted in a descriptive-exploratory way. Two-sided confidence intervals (CIs) will be displayed for important variables. Appropriate methods will be used to derive confidence intervals, depending on data nature and distribution. All safety and tolerability data will be presented in a purely descriptive manner as outlined below.

## **8. STATISTICAL ANALYSIS**

### **8.1 Disposition of Subjects and Withdrawals**

Patients without any documented application of any study medication (without any documented infusion) will be excluded from all statistical analyses, but will be displayed in all data listings.

- The disposition of patients with regard to
  - enrolment of 1st patient and last follow-up of last patient
  - the number of patients enrolled (=subjects who gave informed consent),
  - number of study centres
  - number of enrolled patients by study centre
  - the number and percent of patients who discontinued prematurely within the study period,
  - the number and percent of patients who completed the study by treatment group and study centres.

will be summarised by means of frequency tables.

- For patients with a premature discontinuation the frequency of reason for discontinuation due to
  - AE
  - SAE
  - Withdrawal of consent
  - Investigator decision
  - Death
  - Termination criterion arose: Specification
  - other

will be summarised by treatment group and study centres.

In addition, all treated patients who discontinued prematurely from the study treatment and/or the study (according to the corresponding CRFs) will be listed; at least the time-point of discontinuation and the main reason for discontinuation.

- Analysis population

Inclusion/Exclusion criteria will be listed in the individual listing of raw data

Adherence to the protocol will be described by

- number and percent of patients with at least one deviation from the protocol
- number and percent of patients with at least one major deviation from protocol
- number and percent of patients with major deviations from protocol by type of protocol deviation
- number and percent of patients adhering to each analysis population

using frequency tables

## 8.2 Demographics and Baseline Characteristics

Demographic data and all other important characteristics assessed at the Screening visit (Visit 1) will be presented for the Safety, Intention-To-Treat and Per-Protocol analysis set. The results will be presented in a descriptive way.

Laboratory assessments at the Screening visit will be evaluated in the Safety analysis section.

### 8.2.1 Demographics

Demographic variables will be evaluated from the Screening assessment (Visit 1).

- Continuous demographic variables (age, height, weight) will be summarized using usual descriptive statistics.
- Nominal data (ethnic origin, gender and hormone status) and ordinal data (age classes) will be summarized by means of absolute and percent numbers.

A homogeneity analysis will be performed for the ITT and PP population.

### **8.2.2 Baseline characteristics – Anamnesis**

The following categorical baseline data will be analyzed descriptively by means of absolute and percent numbers

- Medical history  
Pre-existing diseases including surgeries/interventions for the last 3 months will be described presenting
  - number and percent of patients with previous diseases or surgeries if documented
  - frequency distribution of diseases and surgeries as reported by the investigator

and will be summarized by means of frequency tables.

A homogeneity analysis will be performed for number of patients with previous diseases or surgeries for the ITT and PP population using statistical tests as appropriate.

### **8.2.3 Baseline characteristics – Physical examinations**

- Results of physical examination, assessment of
  - heart (normal/abnormal)
  - lung (normal/abnormal)
  - abdomen (normal/abnormal)
  - oedema (normal/abnormal)

will be described presenting number and percent of patients with abnormal findings and summarized by means of frequency tables.

A homogeneity analysis will be performed for physical assessment (using Fisher's exact test) for the ITT and PP population.

### **8.2.4 Previous and concomitant medication**

The following classification of medication taken for the last 3 months will be performed:

- a) Previous medication - discontinued before start of treatment
- b) Previous medication - continued at start of treatment (infusion)

Previous and concomitant medication will be described presenting

- number and percent of patients
- type of medication (as reported)
- type of medication (ATC4 level) by indication (Preferred Term)

and summarized by means of frequency tables.

A homogeneity analysis will be performed for number of patients with previous and concomitant medication of categories a) and b) using Fisher's exact test for the ITT and PP population.

### **8.2.5 Risk factors**

The following risk factors were assessed at the Screening visit:

- Blood pressure  
will be summarized by means of descriptive statistics.
- Physical exercises >30 min/week  
will be summarized by means of frequency tables
- Laboratory values
  - Glucose (fasting) [mg/dL]
  - HbA1c [mg/dL]
  - Cholesterine [mg/dL]
  - HDL [mg/dL]
  - LDL [mg/dL]
  - Triglyceride [mg/dL]will be summarized by means of descriptive statistics

- Smoking habits
  - Type of smoker (smoker, ex-smoker, non-smoker)
  - Smoking period (duration in years)
  - Number of cigarettes per day with the classes <5 cigarettes, 5-<10 cigarettes, 10-<20 cigarettes, 20-<30 cigarettes, 30-<40 cigarettes, 40-<50 cigarettes, >50 cigarettes, other

will be summarized by means of frequency tables

- Alcohol consumption

consumption of

- beer with the classes (none, <250mL, 250-500mL, 500mL-1000mL, >1000mL, other)
- wine with the classes (none, <100mL, 100-250mL, >250mL, other)
- spirits with the classes (none, <10mL, 10-20mL, >20mL, other)

will be summarized by means of frequency tables

A homogeneity analysis will be performed for the risk factor parameters using Fisher's exact test, Wilcoxon test and Mantel-Haenszel test for the ITT and PP population.

### 8.2.6 Bleeding

The following assessments of bleeding will be evaluated exploratory using descriptive methods of statistics.

- Reduction in haemoglobin level
  - by at least 20 g/L
  - by at least 50 g/L
- Requiring transfusion
  - of  $\geq 2$  units of blood
  - of  $\geq 4$  units of blood
- Symptomatic bleeding in a critical area of organ
  - Intra-ocular
  - Intra-spinal
  - Intra-musculär
  - Retro-peritoneal
  - Intra-articular
  - Pericardial

- Subdural intra-cranial
- Intra-cerebral
- Other symptomatic bleeding
  - Gastrointestinal
  - Other organ
- Involving hypotension
- Surgery necessary
- Fatal

A homogeneity analysis of bleeding parameters will be performed using Fisher's exact test for the ITT and PP population.

### **8.2.7 Electrocardiography**

Parameters examined are heart rate, type of rhythm, clinically significant ST-segment deviation and interval times.

- Heart rate [beats/minute]  
will be summarized by means of descriptive statistics.
- Type of rhythm
  - Sinus rhythms
  - Atrial fibrillation
  - Other rhythmwill be summarized by means of descriptive statistics.
- Clinically significant ST-segment deviation  
will be summarized by means of descriptive statistics.
- Interval times
  - P [ms]
  - PQ interval [ms]
  - QRS complex [ms]
  - QTc [ms]will be summarized by means of descriptive statistics.

A homogeneity analysis will be performed for the parameter heart rate using the Wilcoxon test, type of rhythm using the Mantel-Haenszel test and interval times using the Wilcoxon test for the ITT and PP population.

### **8.2.8 TCD**

The result of the TCD central assessment ([name], Münster) is a key element for the efficacy analysis of the study, see 8.4

The technical possibility to perform TCD (sufficient bone window) determines whether a patient is eligible for the study.

- TCD assessment was successful

Due to high rate of no microembolic signals we abandoned the criterion that if no microembolic signal was detected during the recording period then the patient was rated not eligible during the course of the study. In the further course of the study patients were included irrespective whether they present with microemboli or not.

### **8.2.9 DWI-NMR of eligible patients**

Number of cerebral lesions in perfusion area of carotid artery stenosis is determined by a central reading lab ([name], Tübingen).

- back, front right and front left

Classes will be built for the number of lesions

0, 1, 2, 3-5, 6-10, >10

A homogeneity analysis will be performed for the number of cerebral lesions using the Mantel-Haenszel chi-square test for the ITT and PP population.

## **8.3 Duration of infusion**

At Visit 2 study medication was administered by intravenous infusion for 20 minutes. As the start and end time of administration is documented the duration of infusion can be calculated.

- Duration (in minutes) of infusion will be summarized using descriptive statistics.

Comparability of groups will be assessed on base of duration of infusion using non-parametric Wilcoxon tests.

## 8.4 Efficacy analysis

All statistical tests will be performed two-sided and will be interpreted in a descriptive-exploratory way. Test for numerical data will be performed under normality assumptions using ANOVA. In addition normality of distribution will be checked based on goodness of fit tests. If normality can not be assumed sensitivity analyses will be performed using the Wilcoxon test. Two-sided confidence intervals (CIs) will be displayed for important variables. Appropriate methods will be used to derive confidence intervals, depending on data nature and distribution.

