### 8.4.2 Rate of MES per hour (before and after treatment, before CEA)

The rate of MicroEmbolic Signals (MES) as assessed at Visit 1 and at Visit 3 will be summarized using descriptive statistics. Data will be analysed from the central reading lab.

Groups will be compared for

- difference of MES at Visit 1 versus post treatment at Visit 3 (delta MES) and
- percent change of MES at Visit 3 compared to Visit 1 (delta MES)

using the ANOVA.

In a subgroup analysis, only patients will be compared who did not receive any change in the concomitant medication with anti-platelet activity (=rescue medication) between the initial assessment at V1 and the follow-up investigation at V3 / V5.

In addition normality of distribution will be checked based on goodness of fit tests. If normality can not be assumed sensitivity analysis will be performed using the Wilcoxon test.

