#### **8.4.4 Cerebral lesion analysis by DWI-NMR 1 day after CEA and correlation to neurological status**

Cerebral lesions: Number of cerebral lesions in perfusion area of carotid artery stenosis assessed at Visit 5 by the central reading lab ([name], Tübingen).

- back
- front right
- front left
- and total

Groups will be compared for

- change of number of DWI lesions V5 compared to V1 (delta number of lesions)
- percent change of number of DWI lesions V5 compared to V1

using ANOVA.

In addition groups will be compared for

- rate of incidence of patients with DWI lesions after treatment (V5)
- rate of incidence of patients with new DWI lesions after treatment (V5)
- rate of patients with DWI lesions in V5 reduced compared to V1

using Fisher's exact test.

Neurological status: Modified Rankin Scale (MRS) assessed at Visit 6:

0	No symptoms at all
1	No significant disability despite symptoms; able to carry out all usual duties and activities
2	Slight disability; unable to carry out all previous activities, but able to look after own affairs without assistance
3	Moderate disability; requiring some help, but able to walk without assistance
4	Moderately severe disability; unable to walk without assistance and unable to attend to own bodily needs without assistance
5	Severe disability; bedridden, incontinent and requiring constant nursing care and attention
6	Dead

The following correlations will be performed by treatment group:

- Cerebral lesions of back area of carotid artery stenosis x MRS
- Cerebral lesions of front right area of carotid artery stenosis x MRS

Statistical Analysis Plan  
Test product: Revacept  
EudraCT number: 2011-001006-10  
Date 10.06.2019

- Cerebral lesions of front left area of carotid artery stenosis x MRS

Correlation analysis will be performed by calculating the Pearson correlation coefficient. In a subgroup analysis, only patients will be compared who did not receive any change in the concomitant medication with anti-platelet activity (=rescue medication) between the initial assessment at V1 and the follow-up investigation at V3 / V5.

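### The exploratory MES and DWI count analyses lead with ANOVA on raw and percent change; the rank test should lead, without a normality pre-test, and percent change should be dropped

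*SAP*

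**What the plan says.** SAP 8.4 sets the rule for all numerical efficacy variables: "Test for numerical data will be performed under normality assumptions using ANOVA". It continues: "In addition normality of distribution will be checked based on goodness of fit tests". No test or threshold is named. The rank test comes third and conditionally; 8.4.2 repeats the clause for MES: "If normality can not be assumed sensitivity analysis will be performed using the Wilcoxon test".

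Section 8.4.2 compares groups by ANOVA on the raw V1-to-V3 difference in MES and on its percent change. Section 8.4.4 does the same for DWI lesions from V1 to V5, starting with "change of number of DWI lesions V5 compared to V1 (delta number of lesions"). It does not repeat the Wilcoxon clause, so only the general rule in 8.4 covers it.

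On the distribution of MES, SAP 8.2.8 says: "Due to high rate of no microembolic signals we abandoned the criterion". MES-negative patients were admitted from then on. Section 3.3 gives low MES incidence as the reason for the exploratory redesign. Neither section gives a percentage. For DWI, 8.2.9 groups baseline lesion numbers into classes from 0 to more than 10.

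The first-listed endpoint (8.4.1) is different. It is the proportion of patients with fewer MES at V3 than at V1, tested by Fisher's exact test with risk differences and 95% confidence intervals. The SAP uses the term prime analysis there. All tests are exploratory, and SAP 7.5 states that no confirmatory hypotheses are to be tested.

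**The concern.** MES per hour is a count, and the SAP already knows that many of its values are zero. Normality of its change is not an open question that a goodness-of-fit test needs to settle. When the test rejects, ANOVA on the raw scale remains the lead result, so the pre-test adds a data-dependent step without changing what is reported first. Elsewhere the SAP uses the Wilcoxon test with no pre-test, for infusion duration (8.3) and for changes in vital signs (8.5.1).

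At stake are precision and stability. The Fisher endpoint in 8.4.1 uses only the direction of change, so 8.4.2 is where the size of an MES reduction is measured. The trial compares two doses, and the protocol synopsis foresees combining its data with those of later studies. A mean difference that one or two patients can move is a weak basis for either use.

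Percent change adds a second problem. It does not exist for a patient with a zero baseline count, and neither section says what happens to such patients.

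**Working it through.** **No plan figure to reproduce.** SAP 3.3 gives 50 patients per arm (3 × 50 = 150) but no rates, effect, alpha or power, and no MES distribution. Every figure below is therefore conditional on assumed distributions.

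**Leverage on a mean.** One patient whose count changes by D moves a 50-patient arm mean by D/50. A change of 50 signals in one patient moves it by 50/50 = 1 signal per hour.

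**Three-arm simulation** (3 × 50, 1,000 trials per scenario, two-sided 5%). A share of patients has a gamma-distributed MES rate and the rest have rate zero. Counts are Poisson at V1 and V3 with lognormal day-to-day variation, and the same rate ratio applies in both dose arms. The share MES-positive at V1 was about 32–79% across scenarios. The rank test is Kruskal-Wallis, the three-group form of Wilcoxon. Power in one run:

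| Share with MES | Gamma shape | Mean rate | Rate ratio | Log SD | Raw ANOVA | Rank test | ANOVA on log(1+count) |
|---|---|---|---|---|---|---|---|
| 0.4 | 0.7 | 6 | 0.5 | 0.5 | 23% | 31% | 37% |
| 0.6 | 0.5 | 8 | 0.4 | 0.7 | 30% | 47% | 60% |
| 0.6 | 0.3 | 15 | 0.3 | 0.7 | 29% | 65% | 79% |
| 1.0 | 0.7 | 6 | 0.5 | 0.5 | 58% | 73% | 82% |
| 0.6 | 0.5 | 8 | 0.4 | 1.0 | 15% | 32% | 40% |

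- Gain of the rank test over raw ANOVA: 31−23 = 8, 47−30 = 17, 65−29 = 36, 73−58 = 15 and 32−15 = 17 points.
- A repeat of the five scenarios gave 15–57%, 33–73% and 39–82%. The Monte Carlo standard error is at most √(0.5 × 0.5/1,000) = 1.6 points, so gaps of two or three points between runs are expected.
- Absolute power depends on how the variation is coded. Another coding gave 31–81% for raw ANOVA and 41–89% for log ANOVA, in the same order.
- Normality was rejected in 100% of trials.
- In the repeat run one patient of 150 carried a median 21–40% of the residual sum of squares.
- With no effect, all three tests rejected in about 4–6% of trials in the repeat run.

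**Two-arm check, sparser counts** (2 × 50, 3,000 runs; structural zeros 50–85%, mean count 3 or 8 in the others, gamma shape 0.5 or 1, rate ratio 0.4 or 1).

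- At rate ratio 0.4, power was 9–59% for ANOVA and 13–61% for Wilcoxon, a gain of 1–7 points.
- Removing the most extreme patient changed the estimated difference by a median 25–70% and reversed its sign in 2–23% of runs.
- With no effect, rejection was 2.4–5.0% for ANOVA and 4.1–5.2% for Wilcoxon.

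**Percent change** = 100 × (V3 − V1)/V1, which is undefined at V1 = 0. That affects 55–91% of patients in the two-arm scenarios, and 100 − 79 = 21% to 100 − 32 = 68% in the three-arm ones. Small baselines are also lopsided: 1 to 0 is −100%, 1 to 3 is +200%.

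**Why log(1+count) change is not a rate ratio.** A patient with zero at both visits contributes log 1 − log 1 = 0. Suppose half the patients do so, the rest change by log 0.4, and placebo does not change. The back-transformed value is then 0.4^0.5 = 0.63, not 0.4. In the simulation its median was 0.65–0.84 when the true ratio was 0.3–0.5.

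**The case against.** The strongest reply is that the robust test is already planned. If normality is always rejected for MES, the Wilcoxon test will always be run, and only the order of presentation changes. That is largely right for MES. What remains is which result leads, and a pre-test that serves no purpose.

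Second, all these tests are exploratory, with no alpha or power target. That limits the consequences, but in such a trial the estimates are the main product, and here they are fragile.

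Third, a reader might infer several stronger things that the documents do not support:

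- *That a few patients determine the main MES result.* They cannot: 8.4.1 and the V3 prevalence comparison are binary Fisher analyses, untouched by the size of a count.
- *That most MES counts are zero.* The SAP reports a high rate and gives no figure. One scenario above has 79% positive at V1.
- *That false positives are inflated.* They were not in either simulation.
- *That the same size of gain holds for DWI.* Only MES was simulated. Classes from 0 to more than 10 suggest a long tail but do not show many zeros, and V5 imaging follows the intervention, so the change may include procedural lesions. Three Fisher comparisons also accompany the ANOVA there.

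Finally, the gain is not uniform. In the sparser two-arm comparisons, which are closest to a single dose against placebo, it was only 1–7 points.

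**Conclusion.** The point holds for the further exploratory count analyses in 8.4.2 and, by reasoning only, in 8.4.4. Raw-scale ANOVA is a poor lead for MES change. Under the assumed distributions it had about 15–57% power against 33–73% for the rank test in three arms. In the two-arm scenarios with a true effect, the deletion of one patient moved the mean difference by a median 25–70%. The direction was the same in every scenario; the size rests on MES distributions that the documents do not give. The harm is imprecision and lost power. The gap in percent change needs no simulation: it follows from dividing by zero.

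**What to change.** Make the change in the final SAP that accompanies the Blind Review Report, before the blind is broken.

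- **Lead test.** In 8.4.2, and likewise in 8.4.4, make the Wilcoxon test on change the lead comparison for 120 mg, 40 mg and pooled Revacept, each against placebo. Amend the general rule in 8.4 to match and delete the normality trigger for these variables.
- **Description.** Keep raw means and their differences as descriptive results.
- **Effect size, if wanted.** Pre-specify a negative binomial model of the post-treatment count, with log link, treatment, and log(1 + baseline count) as covariate. Report the rate ratio with 95% CI.
- **Supportive test.** ANOVA on change in log(1 + count) may be added, but its back-transformed value must not be reported as a rate ratio.
- **Percent change.** Remove it from both sections.

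The cost is SAP wording and a few lines of SAS; no new data are needed. The downside is that the lead test no longer gives a difference in signals per hour directly, which is why the descriptive means stay.

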### 8.4.1 Reduction of incidence of preoperative microembolic signals

This endpoint is to evaluate whether the rate of patients with incidence of preoperative microembolic signals (MES) was reduced (from Visit1 to Visit 3). Compared will be patients who have been treated with Revacept plus antiplatelet therapy (aspirin or clopidogrel) versus antiplatelet therapy alone (placebo) prior to carotid endarterectomy (CEA). MES data from the central reading lab ([name], Münster) are evaluated.

The evaluation will be performed using a two-sided test of superiority. Groups will be compared for the combined centers using Fisher's exact test.

The sequence of a priori defined hypotheses, with  $\pi$  rate of patients with MES V3 < MES V1 for the specified group, will be:

1)  $H_{01}: \pi_{\text{Revacept 120 mg}} = \pi_{\text{Placebo}}$  VS.

$H_{A1}: \pi_{\text{Revacept 120 mg}} > \pi_{\text{Placebo}}$

2)  $H_{02}: \pi_{\text{Revacept 40 mg}} = \pi_{\text{Placebo}}$  VS.

$H_{A2}: \pi_{\text{Revacept 40 mg}} > \pi_{\text{Placebo}}$

3)  $H_{03}: \pi_{\text{Revacept 120 mg}} = \pi_{\text{Revacept 40 mg}}$

$H_{A3}: \pi_{\text{Revacept 120 mg}} > \pi_{\text{Revacept 40 mg}}$

4)  $H_{04}: \pi_{\text{Revacept 120 mg + 40 mg}} = \pi_{\text{Placebo}}$  VS.

$H_{A4}: \pi_{\text{Revacept 120 mg + 40 mg}} > \pi_{\text{Placebo}}$

Each hypothesis will be tested using Fisher's exact test.

With the first two and the last of hypotheses the test product for a given dose level or overall will be tested against Placebo. With the third hypothesis the higher dose level of the test product will be compared against the lower dose of the test product.

Statistical Analysis Plan  
Test product: Revacept  
EudraCT number: 2011-001006-10  
Date 10.06.2019

All tests will be interpreted exploratively.

The between group risk difference and its 95% confidence interval (CI) will be estimated for each group comparison.

The prime analysis will be based on the ITT population. The PP population will be used for the supportive analyses.

In a subgroup analysis, only patients will be compared who did not receive any change in the concomitant medication with anti-platelet activity (=rescue medication) between the initial assessment at V1 and the follow-up investigation at V3 / V5.

Additionally the prevalence / rate of patients with microembolic signals (>0) at Visit 3 will be compared in a similar manner as in the hypothesis 1- 4

Missing values for the primary analyses at Visit 3 will be imputed by the last observation carried forward approach. This means patients who dropped out before Visit 3 will be counted as non-responder.

An additional analysis of the first endpoint will be performed including the factor center as a stratum. Fisher's exact test will be performed for each stratum and meta-analysis approach will be chosen. Centers with less than 3 patients will be combined into a 'small number of patients' combined stratum.

Individual center results will be presented in a graphical overview with risk differences and their confidence intervals.

**In case of heterogeneities in the baseline parameters**, sensitivity analyses will be performed for the first endpoint using Fisher's exact test and by including the respective parameter as a stratum (binary, ordinal or categorical data). For continuous data these data will be transformed into classes before used as stratum.

A meta-analysis approach will be chosen to pool the stratum dependent results and to investigate for heterogeneity in the strata (e.g. Whitehead, 2003).

The following baseline parameters will be used for the analysis of heterogeneity:

- Demographics
  - Age
  - Height
  - Weight
  - Ethnic origin
  - Gender
  - Hormone status
- Anamnesis – Medical history
  - Number of patients with previous diseases and surgeries
- Vital signs
  - systolic and diastolic blood pressure (right and left arm)

- Physical examination
  - Abnormal findings of assessment of heart, lung, abdomen and oedema (Yes/No)

